Target Population	
Adult subjects aged 50 to 85, inclusive, with a diagnosis of probable dementia with Lewy bodies (DLB), in accordance with Consensus criteria (McKeith, 2005).
 
Subjects included in the study may or may not be receiving other treatments (such as cholinesterase inhibitors and/or memantine) for DLB. If subjects are taking other treatments for dementia and/or hallucinations associated with DLB, the treatment regimen must have been at a stable dose for at least 30 days, and be expected to remain stable during the study.

Number of Subjects Planned	
Approximately 240 randomized subjects
 
RVT-101 70 mg: 80 subjects
 
RVT-101 35 mg: 80 subjects
 
Placebo: 80 subjects

Number of Study Centers Planned	
Approximately 40-50

Study Design	
This is a multi-center, double-blind, randomized, placebo-controlled, parallel-group study in patients with probable DLB. The efficacy and safety of RVT-101 at doses of 70 mg and 35 mg daily will be evaluated over a 24-week treatment period in subjects with probable DLB with or without existing background DLB therapy. All subjects who are on stable doses of other background therapies for dementia and/or hallucinations associated with DLB will continue those regimens unchanged for the duration of the study. Subjects who are not on background DLB therapies at the time of screening will also be eligible for participation. All subjects will refrain from starting additional DLB treatments during the course of the study. The randomization ratio will be 1:1:1 (70 mg RVT-101: 35 mg RVT-101: placebo).
 
Randomization will be stratified according to Baseline MMSE score in the groupings of 14-17 points, 18-21 points and 22-26 points and according to whether subjects are or are not taking a cholinesterase inhibitor as a concomitant medication.
 
During double-blind treatment, there will be weekly clinical assessments for the first two weeks of treatment, bi-weekly assessments until Week 12 and every six weeks thereafter. For certain visits, subjects may have the option of whether to have assessments performed at the clinical study site or by a trained, visiting nurse in their own home.
 
An independent Safety Monitoring Committee (SMC) will review interim safety data accumulated after approximately 30 subjects have

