  - bilateral tubal occlusion
  - vasectomised partner
  - sexual abstinence
  - double barrier method: condom and an occlusive cap (diaphragm or cervical/vault caps) with a vaginal spermicidal agent (foam/gel/film/cream/suppository)
- c) Subjects who have a positive pregnancy test during the study or become pregnant during the study will be discontinued.

Note: Male subjects who are sexually active and whose partner is of child-bearing potential are also required to use an adequate form of birth control including at least 1 barrier method.

- 6) Subject has the ability to comply with procedures for cognitive and other testing in the opinion of the investigator.
- 7) Subject must be able to ingest pills (in tablet form) whole.
- 8) Subject lives with (or has substantial periods of contact with) a regular caregiver who is willing to attend visits, oversee the subject's compliance with protocol-specified procedures and study medication, and report on subject's status, and who has substantial contact with the subject. If the caregiver does not cohabit with the subject, he/she ideally should have a minimum of 10 hours total and at least 3 days contact with the subject per week. Prior to randomization, study staff will review eligibility of non-cohabitating caregivers. Every effort should be made to have the same caregiver throughout the study.
- 9) Subject has provided full written informed consent prior to the performance of any protocol-specified procedure; or if unable to provide informed consent due to cognitive status, subject has provided assent and a legally acceptable representative (LAR) has provided full written informed consent on behalf of the subject.
- 10) Caregiver has provided full written informed consent on his/her own behalf prior to the performance of any protocol-specified procedure.
- 11) The subject's general health status is acceptable for participation in a 24-week study in the opinion of the investigator.

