## **7.6. Compliance with Investigational Product Administration**

When subjects are dosed at the site, they will receive IP directly from the investigator or designee, under medical supervision. The date and time of each dose administered in the clinic will be recorded in the source documents. The dose of IP and study subject identification will be confirmed at the time of dosing by a member of the study site staff other than the person administering the IP.

Subjects and caregivers should be instructed that subjects are to take one tablet of IP from each bottle before bedtime. Subjects and caregivers must be made aware that subjects are not to take two tablets from the same bottle, and are not to combine pills from the two bottles into a single storage bottle. The contents of each bottle must remain distinct. Product administration instructions should be reinforced at each visit.

Every effort should be made to encourage subject compliance with the dosage regimen as per protocol for IP. The investigator is responsible for discussing methods to ensure high treatment compliance with patients and caregivers before randomization. All subjects and their caregivers should be instructed to return IP bottles with any unused drug at each visit to the investigator or designee. A record of the supplies dispensed, taken, and returned will be made in the eCRF at each visit. The investigator or designee is responsible for reconciling the number of tablets returned with the expected number of tablets to be taken by a study subject and accounting for any discrepancies for each of the two bottles.

Subjects should be withdrawn from the study where there has been a failure to take blinded IP for a period exceeding 7 consecutive days. While interruptions in IP administration should be avoided wherever possible, short-term interruptions ( $\leq 7$  days) due to forgetfulness, caregiver

illness or absence, a pause in IP administration required during an intervention, hospitalization, or while a subject considers the study continuation, or for any other reason are not grounds for automatic withdrawal but should be assessed by the investigator.

Other major protocol violations as well as use of excluded drugs (see [Section 7.9.2](#)) may be cause for discontinuation of IP or withdrawal from the study.

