### **7.9.2. Prohibited Medications and Non-Drug Therapies**

Subjects who begin treatment during the study with any prohibited medication, or begin cognitive tasks for cognitive rehabilitation performed under medical supervision or neurostimulation should be withdrawn from the study. However, where such treatment has been for less than or equal to 7 days, termination of the prohibited medication or treatment and continuation in the study may be considered by the investigator in discussion with the Medical Monitor, based on subject safety and the perceived need for the prohibited treatment.

If the subject is receiving one of the conditional medications listed in [Table 1](#), the treatment regimen must have been stable (i.e., no changes in the type of drug, dose or frequency of dosing) for at least 30 days prior to the Screening Visit. In addition, the treatment regimen of these conditional medications should be kept stable during the study, if possible. If treatment with a conditional medication is initiated during the study and will be prescribed chronically, the investigator should discuss this with the Medical Monitor before determining whether to continue the subject in the study.

Use of prohibited and conditional medications and treatments must be documented in the Concomitant Medications section of the eCRF. Prohibited and conditional medications are listed in [Table 1](#).

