**Table 1 Prohibited Concomitant Medications**

PROHIBITED MEDICATIONS: Not allowed during the study or within 5 half-lives prior to the Screening Visit	CONDITIONAL MEDICATIONS: Stable regimen (drug, dose and dosing frequency) for at least 30 days prior to the Screening Visit; dosing regimen during the study should be stable, if possible

 
• Butyrophenones, phenothiazines, and other “conventional” antipsychotics
 
• Barbiturates
 
• MAO inhibitors, including selegiline (Exception: selective MAO-B inhibitors such as rasagiline are allowed)
 
• Any investigational drug
 
• Substrates of CYP2C9 with narrow therapeutic indices: warfarin, phenytoin and (R)-acenocoumarol (active component of some non-warfarin anticoagulants)
 
• Potent CYP3A4 inhibitors/inducers such as ketoconazole, itraconazole, erythromycin, rifampicin, phenytoin and carbamazepine
 
• Known potent Pgp inhibitors (itraconazole, ketoconazole, cyclosporin, diltiazem, verapamil, quinidine, and carvedilol)
 
	
 
• Acetylcholinesterase inhibitors (i.e., donepezil, galantamine, rivastigmine, tacrine)
 
• Memantine
 
• Axona® (caprylidene)
 
• Antidepressants (other than MAO inhibitors)
 
• Thyroid hormones
 
• Atypical antipsychotics (e.g., quetiapine)
 
 
Note: Clozapine is allowed, but must be stable for at least 5 months prior to Screening. In addition, the subject must not have had any episodes of neutropenia or severe infections since starting clozapine as confirmed by the clozapine-prescribing physician and must follow the clozapine prescribing information with regards to monitoring of white blood cell count. Benzodiazepines and other sedatives/hypnotics, including melatonin and sedating antihistamines
 
Note: Intermittent (as needed) use of benzodiazepines and other sedative/hypnotics is allowed only if the drug has a half-life of less than six hours and it is not taken within 5 half-lives prior to cognitive testing.

Abbreviations: CNS = central nervous system; MAO = monoamine oxidase; Pgp = permeability glycoprotein.

Notes:

 RVT-101 affects CYP2C9 substrates.

 CYP3A4 is a major enzyme involved with the metabolism of RVT-101.

 Pgp inhibition may affect CNS levels of RVT-101.

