- Completers (CS) Population: ITT subjects who have completed the Week 24 visit with non-missing endpoints for all three variables, the UPDRS-III, ADAS-Cog 11, and CIBIC+. This population will be used for supportive analysis of all efficacy variables except the UPDRS variables.
- UPDRS Completers Primary Analysis Population: UPDRS Primary Analysis Population Patients who have a Week 24 UPDRS Part III value. This will be run only on the UPDRS Part III and Part 5 variables.
- Pharmacokinetics (PK) Population: All subjects in the Safety Population who undergo plasma PK sampling and have at least one post-baseline evaluable PK concentration result.
- Per-Protocol (PP) Population: Subjects in the ITT Population who have no major protocol violations. The PP Population will not be analyzed if this population comprises more than 95% or less than 50% of the ITT Population. This population will be used for confirmatory analysis all efficacy variables except the UPDRS variables. The PP Population will be identified prior to breaking the study blind. Major protocol violations will be defined as follows:
  - Subject had >7 consecutive days interruption in double-blind study medication

- Treatment with excluded concomitant medications during the double-blind treatment period.
  - If taking an acetylcholinesterase inhibitor, subject had a change in AChEI dose or frequency during the double-blind treatment period.
  - Significant study drug administration errors.
  - Invalid baseline primary or secondary efficacy assessment.
  - Subject does not have MMSE score 14-26 inclusive at Screening and Baseline
  - Subject's baseline MMSE declined by 4 or more points from Visit 2 (Run-in) to Baseline
  - Evidence of other causes of dementia other than DLB as the primary cause
  - History or presence of significant medical or psychiatric condition at Screening.
  - Subject does not live with (or have substantial Periods of contact with) a regular caregiver [at least 10 hours total and at least 3 days per week]).
  - Subject is <80 % compliant or > 120% compliant between Visit 11 (Week 18) and Visit 12 (Week 24) with study drug. Patients who fail to return their bottle (and thus compliance cannot be determined) will be assumed to have been compliant for purposes of the Per Protocol population.

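### The Per-Protocol lists make a cholinesterase-inhibitor dose change a major violation but do not name a new start

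*SAP*

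**What the plan says.** SAP Section 7.4 defines two Per-Protocol populations, one for the non-UPDRS efficacy variables and one for the UPDRS variables. Each has its own list of major protocol violations, and the two lists carry the same items. Two of these items concern concomitant medication:

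- "If taking an acetylcholinesterase inhibitor, subject had a change in AChEI dose or frequency during the double-blind treatment period"
- "Treatment with excluded concomitant medications during the double-blind treatment period"

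The SAP does not say which medications are excluded. The nearest protocol wording is in Section 7.6, where "Other major protocol violations as well as use of excluded drugs" may lead to discontinuation; that sentence points to Section 7.9.2. Table 1 in that section has a prohibited column and a conditional column, and acetylcholinesterase inhibitors stand in the conditional one.

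The protocol speaks twice on starting such a drug. The summary says: "All subjects will refrain from starting additional DLB treatments during the course of the study". Section 7.9.2 provides for the case: "If treatment with a conditional medication is initiated during the study and will be prescribed chronically", the investigator is to consult the Medical Monitor before deciding whether the subject continues.

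On caregivers, inclusion criterion 8 says of a non-cohabiting caregiver that "he/she ideally should have a minimum of 10 hours total and at least 3 days contact with the subject per week", and staff review such caregivers before randomization. The SAP lists as a major violation: "Subject does not live with (or have substantial Periods of contact with) a regular caregiver", followed by the same 10 hours and 3 days in brackets, without the softening word.

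**The concern.** A Per-Protocol set is meant to remove subjects whose conduct on study departs from the plan in ways that could affect the outcome. Here the rule catches an adjustment of existing inhibitor therapy but does not name the addition of that therapy to a subject who had none. Protocol Section 3.1.1 credits these drugs with robust superiority over placebo in DLB, including on cognition, and inhibitor use is a randomization stratum. A new start is therefore at least as relevant to ADAS-Cog 11 and CIBIC+ as a dose change.

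For those two endpoints the Per-Protocol set is the only analysis population with any rule about inhibitor changes. The ITT and Completers definitions have none. If the list is applied literally, the confirmatory analysis does not do what it appears intended to do. If it is applied by judgement, the classification of new starters is not fixed in advance.

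**Working it through.** The plan states no figure on this point, so there is none to reproduce. The check is a comparison of texts.

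**Step 1. Run each on-study event through the two medication items.**

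| Event in the double-blind period | Inhibitor item | Excluded-medication item | Result as written |
|---|---|---|---|
| Existing user changes dose or frequency | Named | Not needed | Major violation |
| Non-user starts an inhibitor | Applies only to those already taking one; a start is not named | Conditional drug; term undefined | No item clearly applies, so the subject stays in |
| Existing user switches to another inhibitor | Type of drug not named; caught only if dose or frequency is also held to differ | As above | Unclear |
| Existing user stops | Caught only if stopping is read as a change to zero dose | As above | Unclear |
| Any subject takes a drug from the prohibited column | Not relevant | Covered | Major violation |

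**Step 2. Test whether the excluded-medication item could reach a new start.** Section 7.9.2 treats the two columns differently. A subject who begins a prohibited drug should be withdrawn, subject to a 7-day allowance. A subject who begins a conditional drug for chronic use is referred for discussion. The term cannot mean all of Table 1, because stable inhibitor users are eligible and form a stratum. It could reach a new start only if it means a conditional drug without the required 30 days of stable use before Screening, and no passage says so. That reading would also make a new antidepressant or thyroid hormone a major violation.

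**Step 3. Compare with how the documents word similar rules.** In the same SAP section, the anti-parkinsonian definition covers an increase in dose, an increase in frequency, and commencement. Protocol inclusion criterion 3 defines a stable regimen by type of drug, dose and frequency. The inhibitor item has dose and frequency only. The authors named a start where they meant one, which points to an omission here.

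**Step 4. Check whether a few subjects could matter.** The Per-Protocol analysis is run only if the set is between 50% and 95% of ITT. Assume that all of the approximately 240 randomized subjects qualify for ITT:

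- upper limit: 0.95 × 240 = 228, so at least 240 − 228 = 12 subjects must be excluded;
- lower limit: 0.50 × 240 = 120.

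With an assumed ITT of 200, the upper limit is 0.95 × 200 = 190 and the minimum is 10. Near the upper limit, the classification of a few subjects could decide whether the analysis is run. The documents give no count of new starters, so this shows sensitivity, not size.

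**Step 5. Compare the caregiver items.** A non-cohabiting caregiver below 10 hours or 3 days can be accepted under inclusion criterion 8 after staff review, and the subject is then a major violator under the SAP. Cohabiting caregivers are unaffected.

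**The case against.** The strongest reply is that the SAP nowhere says new starters are kept. The term for excluded medications is open, the protocol's own use of it points to the whole of Section 7.9.2, and an inhibitor begun on study cannot have been stable for 30 days before Screening. On that view the item already removes new starters and the problem is only clarity. The reading is possible, but it is written nowhere, and Section 7.9.2 separates prohibited from conditional drugs. What stands is that the result is an inference from a closed list, not a stated intention.

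Secondly, conclusions for ADAS-Cog 11 and CIBIC+ rest on the ITT population (SAP Section 9.1), and no testing gate depends on the Per-Protocol set. This stands and limits the point.

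Thirdly, the two protocol statements on starting DLB treatment can be read as expected conduct followed by handling of departures from it. That is fair. They still leave unclear whether a start that is allowed to continue counts as a violation, so they should be reconciled.

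Fourthly, a Per-Protocol set may properly be stricter than eligibility. The bracketed figures give substantial contact an objective cutoff, and several scales depend on the caregiver. This also stands. A reader might infer that the caregiver item is an error that mislabels eligible subjects; the documents show only a difference in strictness, which may be deliberate.

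**Conclusion.** The inhibitor item is defective as written in both Per-Protocol lists. A dose or frequency change is a major violation, a start is not named, and switching and stopping are unclear. This rests on reading the lists as closed and on taking excluded medications not to include conditional ones; the second is the more natural reading but is not stated.

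The reach is limited to the supportive Per-Protocol analyses. The primary analysis, the ITT analyses and the testing order are untouched. A reader might infer that new starts on placebo would mask a cognitive effect by a calculable amount. The documents do not support that. The shift would be the between-arm difference in the proportion starting, multiplied by the effect of a start on the score, and neither input is given. A reader might also infer that memantine belongs in the item. It is another conditional drug, but the SAP item singles out the class used for stratification, and adding memantine goes beyond repairing it.

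The caregiver difference is minor and calls for confirmation of intent.

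**What to change.** Before unblinding, make these changes in both Per-Protocol lists of SAP Section 7.4:

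1. Replace the inhibitor item with: *Subject started, stopped, switched, or changed the dose or frequency of an acetylcholinesterase inhibitor at any time in the double-blind treatment period.*
2. Define excluded concomitant medications as those in the prohibited column of protocol Table 1.

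Separately, the sponsor should reconcile the protocol summary with Section 7.9.2 on starting DLB treatment; which clinical rule applies is for the sponsor to settle. It should also confirm in the SAP whether 10 hours and 3 days of caregiver contact is intended as a Per-Protocol requirement stricter than inclusion criterion 8.

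The cost is SAP wording and a programming rule. Drug name and dates of administration are already the minimum concomitant-medication record (protocol Section 7.9.1), and caregiver hours and days are already to be tabulated (SAP Section 8.3). The downside is a possibly slightly smaller Per-Protocol set, to be considered alongside the 50% to 95% condition.

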IP for the Double-Blind Treatment Period (Weeks 0 to 24) will be supplied at Visits 3, 6, 8, 10, and 11. At each dispensing visit during the Treatment Period, subjects will be given an IP kit containing 2 bottles of IP. Depending on treatment assignment, subjects will receive either two bottles of 35 mg RVT-101 tablets, one bottle of 35 mg RVT-101 tablets and one bottle of placebo tablets, or two bottles of placebo tablets. Each bottle will contain 50 tablets, which is sufficient for 4 weeks plus 22 days overage (V3, V6, V8) and for 6 weeks plus 8 days overage (V10 and V12). Subjects will be instructed to take two tablets of IP daily at bedtime with or

without food; this will consist of one tablet from each of the two bottles in the kit. New bottles of IP will not be dispensed at Visits 4, 5, 7, and 9, however, drug accountability will be checked, and subjects will be re-dispensed the IP bottles they received at the previous dispensing visit. All subjects and their caregivers should be instructed to bring IP bottles, with any unused drug, to each visit. It is important that drug accountability is checked individually for each of the two dispensed bottles.

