- UPDRS Per-Protocol (PP) Population: Subjects in the UPDRS Sensitivity Population who have no major protocol violations. The PP Population will not be analyzed if this population comprises more than 95% or less than 50% of the ITT Population. This population will be used for confirmatory analysis of the primary efficacy variable, UPDRS Part III (and Part 5). The PP Population will be identified prior to breaking the study blind. Major protocol violations will be defined as follows:
    - Subject had >7 consecutive days interruption in double-blind study medication
    - Treatment with excluded concomitant medications during the double-blind treatment period.
    - If taking an acetylcholinesterase inhibitor, subject had a change in AChEI dose or frequency during the double-blind treatment period.
    - Significant study drug administration errors.
    - Invalid baseline primary or secondary efficacy assessment.
    - Subject does not have MMSE score 14-26 inclusive at Screening and Baseline
    - Subject's baseline MMSE declined by 4 or more points from Visit 2 (Run-in) to Baseline
    - Evidence of other causes of dementia other than DLB as the primary cause
    - History or presence of significant medical or psychiatric condition at Screening.

- Subject does not live with (or have substantial Periods of contact with) a regular caregiver [at least 10 hours total and at least 3 days per week]).
- Subject is <80 % compliant or > 120% compliant between Visit 11 (Week 18) and Visit 12 (Week 24) with study drug. Patients who fail to return their bottle (and thus compliance cannot be determined) will be assumed to have been compliant for purposes of the Per Protocol population.

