## 8.8. Treatment Compliance

Compliance with study drug will be assessed over the Double-Blind Treatment Period and Run-In Period using drug dispensing records. Treatment compliance will be computed by determining the number of tablets taken relative to the number of tablets expected. Patients are expected to take two tablets per day, one from each of two bottles.

Treatment compliance based on the drug accountability will be calculated as follows:

- compliance (%) = (number of tablets taken)/(number of tablets expected)\*100
  - number of tablets taken = the number of tablets dispensed – the number of tablets returned
  - number of tablets expected = (date of the last dose - date of the first dose+1)

Summary of treatment compliance will be presented by treatment group, between Week 18 and 24 as well as overall. The number and percentage for compliance expressed as a categorical variable (<80%,  $\geq$ 80% to  $\leq$ 120%, and >120%) will be also presented by treatment group.

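### The Per-Protocol percentage-compliance rule covers only Weeks 18-24 and counts unreturned bottles as compliant, so scattered under-dosing stays in the population meant to confirm the effect under adherence

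*SAP*

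**What the plan says.** SAP 7.4 defines two Per-Protocol populations with the same list of major violations. The general one is described thus: "This population will be used for confirmatory analysis all efficacy variables except the UPDRS variables". The UPDRS Per-Protocol Population does the same job for UPDRS-III, the primary endpoint, and for the UPDRS-5. Neither is analysed if it exceeds 95% or falls below 50% of the ITT Population, and both are to be fixed before unblinding.

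Three items on the list concern adherence:

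- The percentage limit: "Subject is <80 % compliant or > 120% compliant between Visit 11 (Week 18) and Visit 12 (Week 24) with study drug". A rider covers missing counts: "Patients who fail to return their bottle (and thus compliance cannot be determined) will be assumed to have been compliant". The UPDRS version carries the same rider, so there too such subjects "will be assumed to have been compliant for purposes of the Per Protocol population".
- The gap rule: "Subject had >7 consecutive days interruption in double-blind study medication".
- "Significant study drug administration errors", with no definition of what counts as significant.

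The last two are not restricted to Weeks 18-24. SAP 8.8 also promises compliance over the whole period: "Summary of treatment compliance will be presented by treatment group, between Week 18 and 24 as well as overall". The Per-Protocol definitions do not use that overall figure.

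**The concern.** A Per-Protocol analysis is useful here only if its members took the drug more or less as assigned. The percentage limit tests the last quarter of treatment. Subjects with no count for that quarter are placed on the compliant side, although the SAP itself says their compliance is unknown.

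For Weeks 0-18, and for anyone whose final bottles do not come back, adherence is screened only by the gap rule and the undefined error rule. Neither is built to detect doses missed here and there. The plan's aim is the effect after 24 weeks of treatment, and the MMRM uses earlier visits as well, so dosing before Week 18 matters to what is estimated.

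At stake is how the confirmatory analyses of the primary and secondary endpoints can be read. If they agree with the main analysis, that says little about adherent subjects. If they show a smaller effect, retained under-dosing is one possible reason. Presuming compliance also enlarges the population and so moves it toward the 95% ceiling above which it is not analysed.

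**Working it through.** **Inputs.** Visit 11 is nominal day 126 and Visit 12 nominal day 168 (Time and Events Schedule). The limits are 80% and 120%, and the gap rule bites only above 7 consecutive days (SAP 7.4). Adherence below means the share of intended daily doses taken.

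**Share of treatment tested.** (168 - 126)/168 = 42/168 = 25%.

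**What the rule retains when bottles are returned.**

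1. 40% of tablets in Weeks 0-18 with no gap over 7 days, then 100%: (0.40 × 126 + 42)/168 = 92.4/168 = 55%. Weeks 18-24 shows 100%, so the subject is retained.
2. Every other day to Week 18 (63 days), then the fewest days that reach 80% of 42 (0.80 × 42 = 33.6, so 34): (63 + 34)/168 = 57.7%. Retained.
3. The extreme: one day on and seven off to Week 18 (16 of 126 days), then 34 of 42: (16 + 34)/168 = 29.8%. The longest gap is 7 days, which does not exceed 7. Retained.

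**What it retains when the final bottles are not returned.** No percentage test applies. One day on and seven off throughout gives 21/168 = 12.5%, and the gap rule is still not broken.

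In each case retention assumes that the pattern is not judged a significant administration error. An 80% limit on the whole period would flag cases 1 to 3. The unreturned-bottle case also needs the presumption of compliance removed.

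**Possible effect on the estimate (illustration only).** The SAP's design figure reproduces. With 70 per group, difference 4, SD 7.5 and two-sided 0.05, 4/(7.5 × √(2/70)) = 3.155, and Φ(3.155 - 1.96) = 88.4%, against 88% stated.

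Now assume that a fraction f of an active arm is under-dosed, gains nothing and is retained, with 70 per group. The difference becomes 4 × (1 - f):

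| f | difference | power |
|---|---|---|
| 5% | 3.8 | 85% |
| 10% | 3.6 | 81% |
| 20% | 3.2 | 71% |
| 30% | 2.8 | 60% |

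For comparison, removing 20% of each arm and keeping the full 4-point difference leaves 56 per group and 81% power. The values of f are assumptions, and zero benefit is the harshest case.

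**The case against.** The strongest defence is that the weeks just before the Week 24 endpoint are a sensible place to measure adherence, that long gaps at any time are already excluded, and that overall compliance will be tabulated by arm for any reader. Per-Protocol is supportive: conclusions rest on the UPDRS Primary Analysis Population for UPDRS-III and on ITT for other endpoints. Retained under-dosing would be expected to pull a superiority estimate toward zero. The examples are constructed, and a stricter rule adds post-randomisation exclusions.

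Most of this stands and limits the weight of the point. It does not justify classing unknown adherence as good. A table of overall compliance also does not change who is in the analysis.

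Three stronger readings are tempting, and the documents do not support them.

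- *Adherence is examined only in Weeks 18-24.* That is true of the percentage limit alone. The gap and error rules have no such restriction.
- *A subject who leaves before Visit 11 cannot fail.* The SAP is silent on how the percentage limit treats such a subject, and the other criteria still apply.
- *Active and placebo bottles are pooled, which dilutes the 35 mg arm and distorts 35 mg against 70 mg.* SAP 8.8 never says that bottles are summed. Its denominator counts days, which fits one bottle. Suppose a 35 mg subject takes 50 placebo and 18 active tablets in 42 days. Against 84 expected tablets that is 68/84 = 81%, with 18/42 = 43% of active doses. As SAP 8.8 is written it is 68/42 = 162%, which is excluded. Taking 50 tablets from one bottle in 42 days also needs at least 8 extra tablets from it. Protocol 7.6 forbids two tablets from the same bottle, and this could count as a significant administration error. The tablets are indistinguishable, so there is no reason to expect the active bottle to be the one neglected. No 35 mg versus 70 mg test is planned.

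**Conclusion.** The point holds in a limited form. In both Per-Protocol populations the percentage limit covers 42 of 168 days and unknown compliance is set to compliant. As a result, subjects at 55% overall adherence, and lower in extreme patterns, can be retained. This makes the Per-Protocol analysis a weak check of the effect under adherence.

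The expected direction is toward no effect, assuming that under-dosed subjects benefit less. A false-positive finding is not the worry, and the primary analysis is untouched. The examples show what the rule permits. How often it would matter cannot be judged, because the documents give no rate of unreturned bottles or of non-adherence. It is a worthwhile, inexpensive improvement to a supportive analysis.

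**What to change.** In both Per-Protocol definitions in SAP 7.4, before the populations are fixed:

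1. Keep the Weeks 18-24 limit and add the same 80-120% limit over each subject's whole double-blind time on study. SAP 8.8 already summarises this overall figure. It would also supply a rule for subjects who stop before Week 18.
2. Delete the presumption of compliance. Where a bottle is not returned, judge the subject on the intervals with returned bottles. Treat a subject with no usable count as not evaluable for Per-Protocol.
3. Reconcile the SAP 8.8 denominator with two tablets per day before applying any limit. If both bottles are counted, perfect adherence over 42 days scores 84/42 = 200%. State there that compliance is calculated per bottle. The counts already exist, since Protocol 7.1 says: "It is important that drug accountability is checked individually for each of the two dispensed bottles", and Protocol 7.6 requires reconciliation for each bottle. This is a clarification and needs no separate finding on pooling.

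The cost is SAP wording and programming on data already collected. The downside is a somewhat smaller Per-Protocol population through more post-randomisation exclusions. Its expected size should be checked on blinded data against the 50% floor, so that the stricter rule does not cancel the analysis.
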